- Use a unique mHealth approach with open-source application coding and a future basis for ecological momentary assessment extending beyond commercial devices that are at risk for becoming obsolete;
- Incorporates emerging technology into a comprehensive care model in obesity care;
- Create collaborations with mHealth technologists and telehealth experts allowing for translation of innovative laboratory-based technologies into practical applications for medically complex populations in rural settings;
- Use mixed-methods to identify factors leading to behavioral change using technology in the study population;
- Apply lessons learned from this study to other disadvantaged, low-income disparity populations.

APPROACH

Study Design: A single-arm, mixed-methods study that will adopt a pragmatic delivery approach to: a) assess the intervention's feasibility/acceptability; b) investigate the potential effectiveness; and c) ascertain outcomes of implementation. We will recruit 30 obese patients from the D-H Weight & Wellness Center (DH-WWC) to participate in a 12-week pilot that includes monthly assessments and qualitative semi-structured interviews.

Study Site: D-H, in Lebanon, NH, serves 1.5 million persons in New Hampshire and Vermont. Demographics mirror a typical rural New England town (95.4% Caucasian⁵⁶). The DH-WWC is a specialty referral-based obesity clinic whose aim is to improve the health and wellness of patients with obesity. The clinic uses the Epic electronic health record (EHR), and has rooms for interviews, assessments, and video-conferencing.

Selection Criteria: For the purposes of this pilot, we limited inclusion criteria to: community-dwelling, English-speaking patients (age 18-65 years; BMI $\geq 30\text{kg}/\text{m}^2$) with home Wi-Fi high-speed Internet and clearance from their clinician. Patients with dementia (lacking consent), bariatric surgery, severe mental or life-threatening illness, substance use, or exercise contraindications⁵⁷ are excluded as these criteria interfere with the possible efficacy of the intervention. Future pragmatic trials will relax the criteria to allow a pragmatic interpretation.

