- Statistical Analyses: We will assess % weight loss and BMI change (primary outcomes), and change in the 6MWT, REAP-S, IPAQ, PROMIS and URICA (secondary outcomes). Linear/non-linear mixed effects models will evaluate weight, BMI and URICA change over time. To account for repeated measures and variation in trajectory over time, models will include random individual-level intercepts and time trends. A significant coefficient for the mean trend over time will indicate changes in outcomes. All data will be included as the models are robust to data missing at random under the assumptions of a linear mixed model. Paired t-tests will assess the change between baseline and follow-up in 6MWT, REAP-S, IPAQ and PROMIS.
- Sample Size Considerations: This pilot study intends to help develop future studies to evaluate recruitment, feasibility, acceptability and outcomes. Given the longitudinal nature of the data, a key parameter driving the future design is the intraclass correlation coefficient (ICC), a measure of dependence between observations taken on the same person. With 30 participants and a mean of 10 observations/person, we should be able to distinguish between a fairly low ICC of 0.15 versus an alternative of 0.34, based on a one-sample hypothesis test with a significance level of 0.05 and a power of 90%⁸⁰. For the primary outcome of % weight loss, using

a SD of 10.1%, the 95% CI would have half width of 3.6% based on our sample of 30, assuming a normal distribution.

Aim 3: Ascertain the extent to which the intervention works within an existing specialty obesity clinic on implementation outcomes such as workflow adoption, organizational change and compatibility.

Objective and Subjective Adoption, Implementation and Compatibility-Level Outcomes:

- Adoption Domain: *Workflow Adoption*: Questions using semi-structured interviews (methods per Aim 1) from the staff's experience with the intervention (whether it enhances/interferes with workflow; sustainability; technical or other difficulties in delivering care) will be explored. *Staff Adoption*: Haug's 12-item *Measure of Evidence-Based Practice Adoption*⁶⁸ assesses stage of change, experience, attitudes, organization barriers and strategies to support evidence-based practices (1-5 point scale - strongly disagree to agree).

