- Implementation Level: *Organizational Change*: General Organizational Index (GOI)⁶⁹ is an interview of 11 domains with a 5-point rating of: program philosophy, commitment, client eligibility and identification, health promotion plan and its treatment, training, process and outcome monitoring, assessment, quality assurance, choice supervision, & penetration. It has reliable inter-rater agreement and internal consistency.
- Compatibility: *Patient Perception of Value*: Two questions will assess *Willingness to Pay (WTP)*⁷⁰ – whether they would pay for telemedicine delivery of the intervention in lieu of in-person travel time or cost.

Data Analysis: We will use mixed-methods to analyze data from Aim 3 as follows:

- Qualitative Data: Interview data will be managed and analyzed using *Dedoose* as described in Aim 1.
- Statistical Analyses: Descriptive statistics (means, medians, 95% CI) for adoption, organizational change will be assessed at follow-up only. Changes in WTP will be estimated using a paired 2-sample t-test.
- Sample Size Considerations: For changes from baseline on WTP, there will be 80% power to detect large differences in change from 0.32 to 0.28 times a SD assuming a range of within-person correlations (0.2-0.4).

Data Management: Our team is experienced in pilot delivery, data management/acquisition, and validation procedures including: a) health coach training; b) continuous feedback; and c) final data editing. The PI and co-l's will meet staff regularly, supervise and identify quality control issues early to address them promptly. Non-HER entered measures will be collected by the RA using REDCap⁸¹, a secure web/tablet based data collection tool. The Analytics Institute manages a DH-WWC patient registry who will facilitate data extraction. Interviews will be recorded in duplicate using a digital tape recorder. Records will be kept in a locked cabinet. Identifiers will be assigned at enrollment and kept behind the D-H firewall, with a password protected linked file. Data will be exported to *Dedoose* and *R* for analysis with complete labeling intact (variables, labels, missing values)

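### The plan claims 80% power for Willingness to Pay, but the stated change of 0.32 to 0.28 SD is half of what 30 paired patients can detect, and power there is about 27%

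*Combined protocol and SAP*

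**What the plan says.** Under Aim 3, Data Analysis, the analysis bullet reads "Changes in WTP will be estimated using a paired 2-sample t-test". The sample size bullet that follows claims "80% power to detect large differences in change from 0.32 to 0.28 times a SD assuming a range of within-person correlations" running from 0.2 to 0.4. It gives no significance level, no sidedness and no allowance for dropout.

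The number of pairs comes from the Approach section. The study is described as "A single-arm, mixed-methods study that will adopt a pragmatic delivery approach", and its size is given by "We will recruit 30 obese patients from the D-H Weight & Wellness Center (DH-WWC) to participate in a 12-week pilot". Table 1 schedules WTP at timepoints 0 and 3 only, so each patient contributes at most one pair.

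**The concern.** With 30 pairs and only a modest correlation between the two measurements, a detectable change of about 0.3 SD is implausibly small. The sentence itself calls these differences large, which fits a change of around 0.6 SD better than one of 0.3 SD.

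This is the only power statement for Aim 3, and WTP is the measure that hypothesis H3 names for perceived value. If the claim is wrong, the design lacks the power stated for it. A reader who trusts the claim could take a non-significant WTP result as evidence against a shift of about 0.3 SD, when the study would miss such a shift nearly three times in four.

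**Working it through.** **Inputs**
- Pairs: n = 30 (Approach, Study Design).
- Test: paired t-test (Aim 3, Statistical Analyses).
- Power: 80%; within-person correlation r = 0.2 to 0.4; stated detectable change 0.32 to 0.28 SD (Aim 3, Sample Size Considerations). The detectable change falls as r rises, so 0.32 goes with r = 0.2 and 0.28 with r = 0.4.
- Significance level: not stated for WTP. Two-sided 0.05 is assumed. The only level stated in the plan is 0.05, for the intraclass correlation test in Aim 2.

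**Check that n = 30 is the intended base.** The plan's two other precision figures reproduce with it:
- Aim 1 proportion: 1.96 × √(0.8 × 0.2 / 30) = 14.3%, as stated.
- Aim 2 weight loss: 1.96 × 10.1% / √30 = 3.6%, as stated.

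**Detectable change, normal approximation.** The SD of a paired change is SD × √(2(1 − r)), so the detectable change in SD units is (z for 0.975 + z for 0.80) × √(2(1 − r)) / √n.
- (1.960 + 0.842) / √30 = 0.5115
- r = 0.2: 0.5115 × √1.6 = 0.647
- r = 0.4: 0.5115 × √1.2 = 0.560

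The printed values do not come out. Half of these results are 0.3235 and 0.2802, which match the printed 0.32 and 0.28.

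**Detectable change, paired t-test (noncentral t, 29 df).** The standardised change needed is 0.529 SDs of the difference. Multiplying by √1.6 and √1.2 gives 0.669 and 0.580 SD.

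**Power at the printed differences, n = 30**

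| r | Stated change | Change ÷ SD of difference | Power, t | Power, normal | Pairs for 80%, t |
|---|---|---|---|---|---|
| 0.2 | 0.32 SD | 0.32 / √1.6 = 0.253 | 26.8% | 28.3% | 125 |
| 0.4 | 0.28 SD | 0.28 / √1.2 = 0.256 | 27.3% | 28.8% | 123 |

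**Other readings tried**
- One-sided 0.05: detectable change 0.59 to 0.51 SD (t); power at the printed values about 39%.
- SD taken as the SD of the change: detectable 0.53 (t) whatever r is, although the sentence makes the figure vary with r; power at the printed values 40% and 32%.
- The two occasions treated as independent samples: 2.802 × √(2/30) = 0.72 SD, which is larger still.
- Correlation needed for the printed values to hold at n = 30: 0.82 and 0.86 (t), or 0.80 and 0.85 (normal), against 0.2 to 0.4 stated.
- 24 pairs, the edge of the plan's criterion of under 20% dropout: detectable 0.76 to 0.65 SD; power at the printed values about 22%.

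**The case against.** The arithmetic is hard to dispute; the case on the other side concerns weight and wording.

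- **Weight.** WTP is a two-item implementation measure in a single-arm pilot. The primary effectiveness outcomes are percentage weight loss and BMI change. The sample of 30 is presented as a recruitment target and was not derived from this sentence. All of that stands and limits the consequence, but it does not make the stated power true.
- **No decision rule.** The plan sets no margin or go/no-go criterion for WTP and speaks of estimating its change. Misreading a null result is therefore a risk for readers, not something the plan prescribes. This also stands.
- **Cause of the factor of two.** Using √((1 − r)/2) in place of √(2(1 − r)) reproduces the printed values exactly. So would counting about 120 observations, for example 30 patients at four timepoints, although WTP is not measured at four. The documents do not show which happened. Either way the sentence is wrong as a statement about change from baseline.
- **Mixed bases.** The exact half belongs to the normal approximation; on the t basis the printed values are 48% of the detectable change. The 27% is the t figure, against 28% to 29% for the normal approximation. The conclusion is the same on both.
- **Unstated significance level.** Two-sided 0.05 is an assumption. One-sided 0.05 still leaves power at about 39%.

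**Conclusion.** The concern holds, and the sentence is wrong as written. Assuming a two-sided 0.05 level and 30 complete pairs, the smallest change detectable with 80% power is 0.67 to 0.58 SD for correlations of 0.2 to 0.4, about twice what the plan states. Power at the stated changes is about 27% instead of 80%, and roughly four times as many pairs would be needed. Nothing elsewhere in the protocol corrects the figure, and every alternative reading checked leaves power at or below about 40% with two-sided testing or with SD as the SD of one measurement. The error is confined to WTP.

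**What to change.** Replace the Aim 3 sample size sentence with wording such as:

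> With 30 paired observations and a two-sided significance level of 0.05, there is 80% power to detect a change in WTP of 0.67 to 0.58 SD (SD of a single measurement) for within-person correlations of 0.2 to 0.4. With 24 pairs the detectable change is 0.76 to 0.65 SD.

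The sponsor should confirm the significance level and sidedness, since the plan gives neither for WTP. A non-significant WTP result should be interpreted against these figures, with the confidence interval for the change reported beside it.

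The cost is one sentence of wording and a less favourable stated figure. Sample size, data collection and the planned test do not change.
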